#### **Non-Study Medications for Treated Subjects**

Non-study medications will be summarized by therapeutic class and preferred name by treatment group and overall for treated subjects and the following medication types and subsets:

- Prior medications: all; migraine standard of care; prophylactic migraine standard of care
- Current medications: all; migraine standard of care; prophylactic migraine standard of care
- DBT concomitant medications (excluding overall treatment group): all; migraine standard of care; prophylactic migraine standard of care.

Medications will be displayed in descending order of rimegepant frequency within therapeutic class and preferred name.

Non-study prophylactic migraine standard of care medications will also be summarized analogously by treatment group for mITT subjects with prophylactic migraine medication use at

randomization. Medications will be displayed in descending order of overall frequency within therapeutic class and preferred name. (This was an adhoc analysis for the CSR.)

### **Non-Study Medications for DB or OL Rimegepant Treated Subjects**

Non-study DB or OL rimegepant concomitant medications will be summarized analogously by treatment group and overall for DB or OL rimegepant treated subjects and the following subsets: all; migraine standard of care; prophylactic migraine standard of care.

Non-study DB or OL rimegepant concomitant medications will also be summarized analogously by subgroup level and overall for all safety subgroups of interest described in Section 6.1.3.3.

### **Non-Study Medications for OL Rimegepant Treated Subjects**

Non-study OL rimegepant concomitant medications will be summarized analogously by subgroup level and overall for all safety subgroups of interest described in Section 6.1.3.4. Medication subsets include the following: all; migraine standard of care; prophylactic migraine standard of care.

### **Non-Study Medications for Follow-up Subjects**

Non-study follow-up medications will be summarized analogously by treatment group and overall for follow-up subjects and the following subsets: all; migraine standard of care; prophylactic migraine standard of care.

## **6.3 Efficacy**

Efficacy endpoints will be assessed by as-randomized treatment group.

Randomization is stratified by prophylactic migraine medication use at randomization (i.e., IWRS randomization stratum; yes or no). Hence, treatment group comparisons of continuous efficacy endpoints will be *adjusted* by prophylactic migraine medication use at randomization, whereas treatment group comparisons of binary efficacy endpoints will be *stratified* by prophylactic migraine medication use at randomization (except in subgroup analyses). If there are sparse data within a stratum, then results may be presented unstratified.

In treatment comparisons of binary efficacy endpoints, CIs will be based on a normal approximation to the binomial distribution using asymptotic standard error (ASE). Otherwise, CIs for continuous efficacy endpoints will be based on the normal distribution. All CIs will be 2-sided.

Select efficacy listings will display efficacy analysis period (i.e., OP, on-DBT, on-OL rimegepant, and follow-up). See Sections 7.4 and 7.5 for the definition of efficacy analysis periods and study days.

The following general by-subject efficacy listings will be provided:

- Subjects excluded from the efficacy analysis for randomized subjects not in the evaluable mITT population sample, including the reason for exclusion (see Section 3).
- Primary and secondary efficacy endpoints for randomized subjects, including the reason for exclusion from the evaluable mITT population sample (see Sections 6.3.1.1 and 6.3.2)
- Exploratory endpoints for mITT subjects (see Section 6.3.3).

### **6.3.1 Reduction in Migraine Days per Month**

Subjects are instructed to report headache status (yes, no), severity (mild, moderate, severe, none), and characteristics (e.g., aura, nausea, vomiting), as well as medication taken to treat headache or during aura, in the eDiary evening report headache log or follow-up headache log recorded every day in the OP, DBT, and OLE phases.

Migraine days per month will be assessed as “migraine days per 4 weeks” to correspond with the 4-week visit schedule. Migraine days per month are based on data from the previous visit to the current visit (i.e., 4-week interval), and are prorated to account for missing migraine reports.

A by-subject listing will present efficacy analysis period and the following from the eDiary evening report headache log and follow-up headache log for enrolled subjects who had a “yes” response to having a headache or an aura-only event: headache status; aura-only event status, headache lasting  $\geq 30$  minutes status; headache start and end dates; headache severity; headache pain features present\* (i.e., unilateral, pulsating, worsen or avoid activity), headache pain characteristics present (i.e., aura, nausea, vomiting, photophobia, phonophobia); medication used to treat headache or during aura\* (i.e., study medication, additional study medication, triptan, ergotamine, other medication). Migraine days, rescue medication days, and MRM days will also be identified in the listing. Parameters marked with “\*” will be displayed only for subjects with a “yes” response to these questions. COVID-19 visit impact code for visits impacted by COVID-19 will be displayed (see Section 9.1.5.2).

Another by-subject listing for treated subjects will present the following: number of migraine days per month by severity (total; moderate or severe) in the OP efficacy analysis period, overall DBT mean, overall OL rimegepant mean, and in each month (i.e., 4-week interval) in the on-DBT and on-OL rimegepant efficacy analysis periods; number of days of efficacy data in the aforementioned intervals, overall DBT mean, and overall OL rimegepant mean; and migraine day values, changes and percent changes from OP in the aforementioned intervals, overall DBT mean, and overall OL rimegepant mean.

See Section 7.6.2.2 for the definitions of efficacy data days and migraine days.

#### **6.3.1.1 Reduction in Migraine Days per Month in the DBT Phase: Primary Efficacy Endpoint**

The number of migraine days per month in the DBT phase will be examined relative to the number of migraine days per month in the OP for evaluable mITT subjects, i.e., subjects with  $\geq$

14 days of eDiary efficacy data (not necessarily consecutive) in both the OP analysis period and  $\geq 1$  month (i.e., 4-week interval) in the on-DBT analysis period.

Months in the DBT phase are defined as follows:

- Month 1 ( $\leq 4$  weeks; study days 1 to 28)
- Month 2 ( $> 4$  to  $\leq 8$  weeks; study days 29 to 56)
- Month 3 ( $> 8$  to  $\leq 12$  weeks; study days 57 to 84)

Analyses will be based on eDiary efficacy dates in the OP and on-DBT efficacy analysis periods.

The number of migraine days per month will be prorated to 28 days and derived as follows:

- OP:  $28 \times (\text{total number of migraine days in the OP analysis period}) / (\text{total number of efficacy data days in the OP analysis period})$ .
- Month (i.e., 4-week interval) in the on-DBT efficacy analysis period:  $28 \times (\text{total number of migraine days in the month}) / (\text{total number of efficacy data days in the month})$ . Subjects must have  $\geq 14$  days of efficacy data (not necessarily consecutive) in the specified month to be evaluable.
- Overall DBT mean:  $28 \times (\text{total number of migraine days through Month 3 in the on-DBT efficacy analysis period}) / (\text{total number of efficacy data days through Month 3 in the on-DBT efficacy analysis period})$ .

### Missing Efficacy Data

Missing efficacy data in the OP and DBT phases will be assessed using the number and percentage of mITT subjects in the following categories:

- Evaluable
- Not evaluable, i.e.,  $< 14$  days of efficacy data in the OP and  $< 14$  days of efficacy data in all 3 months (i.e., 4-week intervals) of the DBT phase
  - $< 14$  days of efficacy data in the OP
  - $< 14$  days of efficacy data in any of the following months (i.e., 4-week intervals) of the DBT phase:
    - Month 1:  $\leq 4$  weeks
    - Month 2:  $> 4$  to  $\leq 8$  weeks
    - Month 3:  $> 8$  to  $\leq 12$  weeks

### Descriptive Analyses

Analyses will be based on evaluable mITT subjects.

---

Values and changes (both absolute and percent) from the OP in the number of migraine days per month in the DBT phase will be summarized descriptively as continuous parameters (including 2-sided normal 95% CIs for mean change) by treatment group and migraine severity in each month of the DBT phase and overall DBT mean. Migraine severity categories are (1) total (mild, moderate, severe, none, or not reported) and (2) moderate or severe.

Values and changes will also be summarized by subgroup level for all efficacy subgroups of interest described in Section 6.1.3.1.

The following scatter plots will be produced by treatment group:

- Change from OP in the number of total migraine days per month in the last month of the DBT phase (y-axis) versus number of migraine days per month in the OP (x-axis)
- Percent change from OP in the number of total migraine days per month in the last month of the DBT phase (y-axis) versus number of migraine days per month in the OP (x-axis)
- Change from OP in the number of total migraine days per month in the overall DBT mean (y-axis) versus number of migraine days per month in the OP (x-axis)
- Percent change from OP in the number of total migraine days per month in the overall DBT mean (y-axis) versus number of migraine days per month in the OP (x-axis).

Plots will include a horizontal reference line at 0. The last 2 plots were included as adhoc analyses in the CSR.

In the percent change analyses, subjects must also have  $\geq 1$  migraine day (i.e., absolute not prorated to 28 days) of appropriate migraine severity in the OP analysis period to be included.

### **Treatment Group Comparisons**

Analyses will be based on evaluable mITT subjects and total migraine severity, unless specified otherwise.

#### Principal Analysis

The principal analysis of the primary endpoint will use a generalized linear mixed effect model with the following variables: change from the OP in number of total migraine days per month as the dependent variable; subject as a random effect; number of total migraine days per month in the OP as a covariate; treatment group, prophylactic migraine medication use at randomization, month (i.e., months 1 to 3 of the DBT phase), and the month-by-treatment group interaction as fixed effects. The model will be repeated by prophylactic migraine medication use at randomization (yes, no). The following model estimates will be reported:

- Least-squares mean (LSM) change from OP, SE, and 95% CI by month and randomization stratum (yes, no, overall) for each treatment group
  - Difference in LSM changes from OP between treatment groups (rimegepant – placebo), SE, 95% CI, and p-value by randomization stratum (yes, no) for each month
-

- Difference in LSM changes from OP between treatment groups (rimegepant – placebo), SE, 95% CI, and p-value for each month. Results in the last month will support the primary objective, results in the first month will support the fourth secondary objective, and results in the second month will support the first exploratory objective.
- Overall LSM change from OP, SE, and 95% CI by randomization stratum (yes, no, overall) for each treatment group
- Difference in overall LSM changes from OP between treatment groups (rimegepant – placebo), SE, 95% CI, and p-value by randomization stratum (yes, no)
- Difference in overall LSM changes from OP between treatment groups (rimegepant – placebo), SE, 95% CI, and p-value. Results will support the second secondary objective.

These analyses will be repeated for moderate or severe migraine severity to support the first exploratory objective. All variables in the model will be the same, except (1) change from the OP in number of moderate or severe migraine days per month will be the dependent variable, and (2) number of moderate or severe migraine days per month in the OP will be the covariate.

A longitudinal plot will display the LSM change in the number of total migraine days from OP per month (y-axis) versus month of the DBT phase (x-axis). Another longitudinal plot will display the LSM change in the number of moderate or severe migraine days from OP per month (y-axis) versus month of the DBT phase (x-axis). Error bars will denote 95% CIs.

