9.4 Primary Endpoint

The change from baseline efficacy endpoint is analyzed using a generalized linear mixed effect model, that includes subject as a random effect, and has the baseline number of migraine days (i.e., during the Observation Period) as a covariate. The model includes fixed effects for: treatment group; stratification factor (use of prophylactic migraine medication); scheduled visit; and the visit by-treatment group interaction. Scheduled visits included in the model are nominally at 4, 8 and 12 weeks. Evaluation of migraine days per month is based on the data from the previous visit to the current visit (i.e., 4-week interval), and is prorated to account for missing migraine reports. A migraine days per month endpoint, prorated to 28 days, will be computed for subjects in the efficacy analysis set who provide at least 14 days of eDiary data during any reporting period (i.e., Observation Period or a 4-week interval during the double-blind treatment phase). The difference estimate (rimegepant - placebo), standard error, 95% confidence interval, and p-value will be reported for the last 4 weeks (Weeks 9 to 12) of the double-blind treatment phase.

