## 5 SAMPLE SIZE AND POWER

With a sample size of roughly 800 subjects randomized, and 400 subjects per treatment group, we expect roughly 370 subjects per treatment group in the evaluable mITT population (i.e., Efficacy Analysis Set in the BHV3000-305 Protocol). Assuming rimegepant provides roughly a 1-day advantage over placebo on the primary endpoint and a common standard deviation (SD) of 3.75 days, then the study will have roughly 95% power on the primary endpoint. The estimates for the change in migraine days per month and the SD are consistent with publicly available information from another investigational oral calcitonin gene-related peptide (CGRP) antagonist for this indication.

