### **6.1.2 Type 1 Error Control**

Type 1 error is controlled through the use of hierarchical testing. The significance of the primary endpoint is evaluated at the 0.05 level. If the primary endpoint is significant, then the following secondary endpoints will be tested hierarchically in the following order, each at the 0.05 level:

1. Proportion of subjects with  $\geq 50\%$  reduction from OP in the mean number of moderate or severe migraine days per month in the last month of the DBT phase
2. Change from OP in the mean number of migraine days per month in the entire DBT phase
3. Mean number of rescue medications days per month in the last month of the DBT phase
4. Change from OP in the mean number of migraine days per month in the first month of the DBT phase
5. Change from baseline in MSQoL restrictive role function score at Week 12 of the DBT phase
6. Change from baseline in MIDAS total score at Week 12 of the DBT phase.

Thus, a secondary endpoint will be tested only if the preceding secondary endpoint in the hierarchy is determined to be significant. Descriptive p-values will be provided for any non-significant secondary endpoints and comparative exploratory endpoints.

---

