#### **Treatment Group Comparisons**

A generalized linear mixed effect model will have the following variables: number of rescue medication days per month as the dependent variable; subject as a random effect; treatment group, prophylactic migraine medication use at randomization, month (i.e., months 1 to 3 of the DBT phase), and the month-by-treatment group interaction as fixed effects. The model will be repeated by prophylactic migraine medication use at randomization (yes, no). The following model estimates will be reported:

- LSM, SE, and 95% CI by month and randomization stratum (yes, no, overall) for each treatment group
- Difference in LSMs between treatment groups (rimegepant – placebo), SE, 95% CI, and p-value by randomization stratum (yes, no) for each month
- Difference in LSMs between treatment groups (rimegepant – placebo), SE, 95% CI, and p-value for each month. Results in the last month will support the third secondary objective, whereas results in the other months will support an exploratory objective.
- Overall LSM, SE, and 95% CI by randomization stratum (yes, no, overall) for each treatment group
- Difference in overall LSMs between treatment groups (rimegepant – placebo), SE, 95% CI, and p-value by randomization stratum (yes, no)
- Difference in overall LSMs between treatment groups (rimegepant – placebo), SE, 95% CI, and p-value. Results will support an exploratory objective.

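### The primary model names only a random subject effect, so the Month 3 and Month 1 tests rest on an equal-variance assumption that no planned analysis checks

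*SAP*

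**What the plan says.** SAP 6.3.1.1 (Principal Analysis) sets out a generalized linear mixed effect model for the change in monthly migraine days. It has "subject as a random effect; number of total migraine days per month in the OP as a covariate", and fixed effects for treatment, prophylactic-medication stratum, month, and month by treatment. Protocol 9.4 describes the same model, one "that includes subject as a random effect, and has the baseline number of migraine days" as covariate. The Month 3 contrast from this fit is the primary result and the Month 1 contrast is the fourth secondary.

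The rescue-medication model in SAP 6.3.2.2 is built the same way: "number of rescue medication days per month as the dependent variable; subject as a random effect". The menstrual-migraine (6.3.3.1) and triptan or ergotamine (6.3.3.3) models follow suit.

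On inference, SAP 6.1.2 says "The significance of the primary endpoint is evaluated at the 0.05 level", with six secondary tests gated behind it. SAP 6.3 bases intervals for continuous endpoints on the normal distribution and adds "All CIs will be 2-sided". No residual covariance structure, robust variance estimator or degrees-of-freedom method is named. SAP 6.1 refers to the Core SAP for descriptive statistics, counting, rounding and coding rules, not for model covariance.

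The one sensitivity analysis of the primary endpoint imputes missing months by jump to reference and then fits the same mixed model.

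**The concern.** A random subject effect with independent, equal-variance residuals is compound symmetry: every month has the same variance and every pair of months the same correlation. The model then estimates one variance from all three months and uses it for each month's treatment contrast. That would suit a test of the three-month average better than a test of a single month, and the primary hypothesis concerns Month 3 alone.

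At stake is the calibration of the confirmatory p-value and interval. If the Month 3 variance is above the three-month average, the reported standard error is too small and the 5% test rejects too often. If it is below, the test is conservative and gives up some power. The Month 1 test errs by the same rule applied to its own variance. The primary test opens the whole hierarchy, so its error rate carries through to the secondary claims.

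**Working it through.** **Inputs.** SAP section 5 gives about 370 evaluable subjects per arm, "Assuming rimegepant provides roughly a 1-day advantage over placebo on the primary endpoint", and "a common standard deviation (SD) of 3.75 days". Alpha is 0.05, taken as two-sided because the intervals are. The SD of 3.75 is attached to the primary endpoint, so it is held as the Month 3 value. SDs for Months 1 and 2 are assumptions, because the documents give none.

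**The plan's own figure.** SAP section 5 states "then the study will have roughly 95% power on the primary endpoint". The standard error is 3.75 × √(2/370) = 0.2757; 1/0.2757 = 3.627; Φ(3.627 − 1.960) = 95.2%. The figure reproduces, and 366 per arm would give 95%.

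**Effect of pooling, complete data.** Write v1, v2, v3 for the monthly variances and v̄ for their mean.

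- True Month 3 standard error: √(2·v3/370) = 0.2757.
- Random-intercept standard error: √(2·v̄/370).
- Ratio: r = √(v̄/v3).
- Actual type I error: 2 × [1 − Φ(1.96·r)].

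Worked example, SDs 3.25/3.5/3.75: v̄ = (10.5625 + 12.25 + 14.0625)/3 = 12.292; r = √(12.292/14.0625) = 0.935; model standard error 0.258; type I error 2 × [1 − Φ(1.832)] = 6.7%.

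| SDs, Months 1/2/3 | r | Model SE | Month 3 type I error |
|---|---|---|---|
| 3.75/3.75/3.75 | 1.000 | 0.276 | 5.0% |
| 3.5/3.6/3.75 | 0.965 | 0.266 | 5.9% |
| 3.25/3.5/3.75 | 0.935 | 0.258 | 6.7% |
| 3.0/3.4/3.75 | 0.906 | 0.250 | 7.6% |
| 4.0/3.9/3.75 | 1.036 | 0.286 | 4.2% |
| 4.25/4.0/3.75 | 1.068 | 0.294 | 3.6% |
| 3.5/3.98/3.75 | 1.000 | 0.276 | 5.0% |

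The last row matters: the months differ, but the Month 3 variance equals the average, so the Month 3 standard error is right.

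In the two falling scenarios the power of the random-intercept test would be 94.5% and 93.7%. With a month-specific variance it stays at 95.2% throughout.

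**Month 1.** Replace v3 by v1. For 3.25/3.5/3.75, r = √(12.292/10.5625) = 1.079 and type I error is 3.5%, so that test is conservative when the Month 3 test is anticonservative.

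**Simulation with dropout.** Null trials used the SAP's fixed effects, 370 per arm, missing-at-random dropout leaving about 91% observed at Month 3, and 25,000 trials per scenario (Monte Carlo error about 0.14 points, since √(0.05 × 0.95/25,000) = 0.0014). Correlations were 0.7 between adjacent months and 0.5 between Months 1 and 3, except in the first row, where all were 0.6.

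| Scenario | Model-based SE | Sandwich SE |
|---|---|---|
| Equal variance, equal correlation | 5.0% | 5.1% |
| Equal variance, unequal correlation | 5.1% | 5.0% |
| Rising, 3.25/3.5/3.75 | 6.9% | 5.1% |
| Rising, 3.0/3.4/3.75 | 7.7% | 5.1% |
| Falling, 4.25/4.0/3.75 | 3.9% | 5.1% |
| Month 3 variance at the average, 3.5/3.98/3.75 | 5.2% | 5.2% |

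The mean Month 3 estimate was within 0.002 days of zero in every scenario. Unequal correlation alone did not matter.

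**The case against.** The strongest reply is that the documents are silent rather than wrong. They do not exclude an unstructured residual matrix or a sandwich standard error, and either would remove the problem. That is fair as far as it goes. But the SAP lists the model's terms, and subject is the only one that links a subject's months. The revision history for version 5.0 records that when the MSQoL and MIDAS models became single-visit models, the random subject effect was taken out. This suggests, without proving it, that the SAP uses that term as its repeated-measures device. An analyst following the text would fit a random intercept.

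The second reply is that nothing in the plan shows the variances to be unequal. This stands, and it rules out stronger readings that a reader might infer:

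- *Partial months pile up in Month 3.* The on-treatment cut-off at last dose plus one day (SAP 7.4) shortens whichever month a subject stops in, not Month 3 in particular.
- *Proration from as few as 14 days inflates the Month 3 variance materially.* Take an extreme case: 8 migraine days a month, independent days, and all 7.5% of subjects (the loss from 400 to 370) with exactly 14 days in Month 3 only. The added variance is 0.075 × 5.71 = 0.43. The Month 3 SD becomes √(14.06 + 0.43) = 3.81, and type I error is 5.2%.
- *Baseline predicts Month 1 better than Month 3.* Neither document says so.
- *Unequal correlations misdirect the handling of dropouts.* The simulation gave 5.1% with a centred estimate.

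It is also fair that the month-by-month descriptive summaries in SAP 6.3.1.1 would let a reader notice unequal spread. Noticing it does not correct the test, and no alternative analysis is planned.

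**Conclusion.** The concern holds in conditional form. As written, the model assumes equal variance over Months 1 to 3, and the Month 3 and Month 1 tests inherit a pooled standard error. Whether that error is material depends on monthly variances that the documents do not give, so neither its size nor its direction can be established from them. For assumed Month 1 SDs between 3.0 and 4.25, with Month 3 at 3.75, type I error at Month 3 is about 4% to 8%.

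A reader might conclude that the primary p-value is wrong, or that it is wrong whenever the months differ. The documents support neither: the Month 3 result is off only if the Month 3 variance departs from the three-month average. The estimate itself is not in question, and the sample-size calculation stands. A standard method removes the assumption at almost no cost, and the jump-to-reference analysis cannot expose it, so this is a change that should be made.

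**What to change.** Specify Months 1 to 3 as a repeated-measures model with an unstructured within-subject covariance and Kenward-Roger degrees of freedom. Name the fallback in advance: heterogeneous Toeplitz, or the random-intercept model with a subject-clustered sandwich standard error. Apply the same structure to the rescue-medication, menstrual-migraine and triptan or ergotamine models, and to the analysis model run after jump-to-reference imputation. Small subgroup levels, such as age 65 or over, would move to the fallback if the model does not converge.

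The statistical cost is four covariance parameters (six instead of two), which is negligible with about 740 evaluable subjects, and the sample size does not change.

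Timing is the real constraint. SAP version 10.0 records changes made after the final database lock, and parts of the text describe analyses already in the clinical study report. Where results have been unblinded, the unstructured fit should be reported as a sensitivity analysis beside the planned model, not put in its place.
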